1. LIST OF ABBREVIATIONS

Abbreviation	Definition
AE	Adverse Event
AEM	Adverse Event Monitoring
BU	Bethesda Unit(s)
CRF	Case Report Form
ED	Exposure Day
eCRF	Electronic Case Report Form
FFP	Fresh Frozen Plasma
HIV	Human Immunodeficiency Virus
ICH	International Conference on Harmonisation
IRB/IEC	Institutional Review Board/Independent Ethics Committee
IU	International Units
IV	Intravenous
MTP	Minimally Treated Patients
PCC	Prothrombin Complex Concentrates
PTP	Previously Treated Patients
PUP	Previously Untreated Patients
SAE	Serious Adverse Event
CFDA	State Food and Drug Administration

Term	Definition
AEM form	Adverse Event Monitoring form
Bleeding episode	Hemorrhage occurring spontaneously or due to injury at 1 or more sites.
Completed subject	Any subject who completes the registry activities through the Registry Completion Visit and who is not withdrawn early.
Cryoprecipitate	Prepared from plasma and contains fibrinogen, von Willebrand factor, factor VIII, factor XIII and fibronectin.
Exposure day	Any calendar day during which the subject receives BeneFIX or other purified human derived FIX product. This excludes FFP, PPC and cryoprecipitate.
Factor IX inhibitor (clinically significant)	Local positive inhibitor and at least one of the following observations within 4 weeks before or 4 weeks following a positive inhibitor result: 
 1. ≥ 2 events indicating a decrease in the efficacy of BeneFIX (or other AE indicating a decrease in the efficacy of the test article) 2. A need to administer alternate hemostatic products or increase the dose or dosing frequency in order to achieve sufficient efficacy
Factor IX inhibitor (local)	A local positive result using either the Bethesda assay (≥ 0.6 BU or $>$ the upper limit of normal) or the Nijmegen modification of the Bethesda assay (≥ 0.6 BU).
Factor IX inhibitor (history of)	A history of factor IX inhibitor (clinical or laboratory-based assessment).
FIX Hypersensitivity Allergic reaction	A hypersensitivity reaction to BeneFIX with symptoms including hives, generalized urticaria, tightness of the chest, wheezing, hypotension, and anaphylaxis.
Fresh Frozen Plasma	Plasma removed from whole blood that involves freezing during the preparation. It contains all coagulation factors in normal concentrations.
Incremental recovery	FIX:C at 30 minutes after infusion, [IU/dL]/[IU/kg]

Investigator	A person, with the appropriate qualifications, responsible for the conduct of the registry at a study site.
Lack of Efficacy/Lack of Effect	Lack of efficacy/effect is the failure of expected pharmacologic action or therapeutic benefit.
MTP	Patients who have received at least one ED but less than or equal to 150 documented prior Factor IX EDs (≤ 150 EDs).
On-demand treatment	Treatment of hemorrhages, as needed, by administering an unscheduled bolus infusion of BeneFIX to stop bleeding and control hemostasis.
Preventive treatment	Factor IX replacement therapy given before an event that could increase the risk of bleeding (e.g. surgery or exercise).
Prophylaxis	Factor IX replacement therapy administered at a routine interval such as every other day, for a prolonged period of time, to prevent occurrence of spontaneous bleeding episodes.
Prothrombin Complex Concentrates	Produced from the cryoprecipitate supernatant of plasma pools after removal of antithrombin and factor XI. Depending on the processing technique, PCCs may contain clotting factors II, IX, X and sometimes VII. To prevent activation of these factors, most PCC contain heparin. PCC may also contain the natural coagulation inhibitors protein C and protein S.
PTP	Patients who have received more than 100 documented prior Factor IX EDs (>150 EDs).
PUP	Patients who have not received any Factor IX products
Registry start date	Date the first registry subject provides informed consent.
Registry end date	Date of last contact with the last subject on the registry.
Regulation	The term regulation refers to all applicable regulations, laws, and guidelines. The regulations may be international, national, or local and may include but are not limited to the Code of Federal Regulations (United States); the European Clinical Trials Directive; the

	International Conference on Harmonisation (ICH) Guideline for Good Clinical Practice; and the World Medical Association Declaration of Helsinki: Ethical Principles for Medical Research Involving Human Subjects.
Treatment Period	Day 0 until study completion/withdrawal

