7.3 Study procedures

A written, Pfizer and institutional review board (IRB)/independent ethics committee (IEC)-approved, informed consent/assent (as appropriate) must be obtained before initiating study procedures.

Informed consent must be obtained from the legal representative of the child or adolescent in accordance with local law before assent is sought. An assent should be obtained from all subjects that have an intellectual age of 7 years or more. All potential pediatric subjects should be informed to the fullest and most appropriate extent possible about the study, in language and terms they are able to understand.

If a subject signed assent for a study, a consent must be signed once the subject turns legal age, based on local requirements.

The eligibility of the subject will be evaluated. After inclusion of the subject and after obtaining written informed consent (prior to any registry-related procedure being performed) from the subject's parents/caregiver/legal representative and assent, if applicable, the investigator or site staff will enter the subject data into source documents and into an electronic Case Report Form (eCRF).

Following the baseline data collection (Day 0), the visits to collect registry study data are at the discretion of the investigator and may follow the local usual standard of care, however, the sponsor recommends safety, treatment data and FIX inhibitor assessments at 6 month intervals at a minimum during the 1 year of participation in the registry. A Follow-up Call is to be conducted at least 28 calendar (+10 days) after the Final/Early Termination visit in order to collect information on the occurrence of adverse events and concomitant medications.

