7.4.2 Treatment Data Collection (Day 0 to 12 months/Early Withdrawal)

All data will be collected in the CRF. This data will be collected following Day 0 through the Registry Completion/Early Withdrawal Visit.

1. Exposure days, bleed, infusion and response data will be collected throughout the treatment period on the subject diaries.
2. The efficacy outcomes data will be:
 - Annualized bleeding rates (ABR) in subjects receiving treatment with BeneFIX,
 - The responses to all on-demand treatment with BeneFIX for all bleeds (4 point scale of assessment),
 - Number of BeneFIX infusions to treat each new bleed
 - Number of spontaneous/non traumatic breakthrough bleeds within 48 hours of a prophylaxis dose of BeneFIX

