7.4.3 Safety Data Collection (Day 0 to 12 months/Early Withdrawal)

Safety data collected throughout the treatment period (Day 0 to 12 months/Early Withdrawal) will consist of:

- All AE and SAE data, including product-related medically important adverse events (inhibitor development, FIX hypersensitivity allergic reactions, thrombogenicity, lack of effect and red cell agglutination,). This data will be reported on the appropriate CRF and AEM forms during treatment with BeneFIX.

- Laboratory results determining the presence of FIX inhibitor antibodies by the Bethesda assay or Nijmegen modification of the Bethesda assay are recommended to be collected for subjects at all study visits.
- Changes in concomitant diseases or medicinal therapy
 1. Medicinal concomitant therapy
- FIX activity and recovery values, if available and assessed at routine clinic visits.

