7.8. Data analysis

Detailed methodology for summary and statistical analyses of data collected in this study will be documented in a Statistical Analysis Plan (SAP), which will be dated, filed and maintained by the sponsor. The SAP may modify the plans outlined in the protocol; any major modifications of primary endpoint definitions or their analyses would be reflected in a protocol amendment.

A statistical sample size calculation will not be performed for this study. Because all eligible and willing-to-participate subjects will be enrolled in the study and no statistical hypotheses are tested.

All safety and efficacy analyses, except the analysis for Annualized Bleeding Rates (ABR), will be performed on all subjects who receive at least one dose of BeneFIX. ABR analysis will be performed on subjects who participated in prophylaxis period for at least 6 months.

The primary safety outcomes to be reported will be development of clinically significant FIX inhibitors, FIX hypersensitivity allergic reactions, thrombogenicity, lack of effect and red cell agglutination.

Secondary safety outcomes include the frequency of adverse events and serious adverse events, etc.

Secondary efficacy outcomes will be:

- Annualized bleeding rates (ABR) in subjects receiving treatment with BeneFIX,
- The responses to all on-demand treatment with BeneFIX for all bleeds (4 point scale of assessment),
- Number of BeneFIX infusions to treat each new bleed,
- Number of spontaneous/non traumatic breakthrough bleeds within 48 hours of a prophylaxis dose of BeneFIX.

The efficacy results of this study will be presented using descriptive statistics. The following descriptive statistics will be used:

- For numeric endpoints: sample size, mean, standard deviation, median, minimum and maximum;
- For categorical endpoints: count and percentage.

Safety data will be tabulated and listed according to Pfizer's standard reporting algorithms. The reasons for discontinuation of BeneFIX therapy will be described.

Subgroup analysis will be done by several sub-populations.

Additional details of the analysis will be provided in the statistical analysis plan and/or the clinical study report. This information may include details of missing and, if applicable, unused and spurious data. Deviations from the statistical plan will be reported in the clinical study report.

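### A dose or frequency increase in the 4 weeks after a positive test can confirm a clinically significant inhibitor, but no section requires dose data to be recorded after the final visit, where the last recommended test is taken

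*Protocol*

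**What the plan says.** Section 7.8 names the outcome first among the primary ones: "The primary safety outcomes to be reported will be development of clinically significant FIX inhibitors". Section 1 defines it as "Local positive inhibitor and at least one of the following observations within 4 weeks before or 4 weeks following a positive inhibitor result". Two kinds of observation qualify:

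- Criterion 1: two or more "events indicating a decrease in the efficacy of BeneFIX (or other AE indicating a decrease in the efficacy of the test article").
- Criterion 2: "A need to administer alternate hemostatic products or increase the dose or dosing frequency in order to achieve sufficient efficacy".

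On data collection, Section 7.4.2 states "Exposure days, bleed, infusion and response data will be collected throughout the treatment period on the subject diaries", and sets the end point: "This data will be collected following Day 0 through the Registry Completion/Early Withdrawal Visit". Section 1 likewise ends the treatment period at study completion or withdrawal.

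On testing, Section 7.4.3 says that inhibitor results "are recommended to be collected for subjects at all study visits". Sections 7.2.2 and 7.3 recommend visits and assessments at least every 6 months, with a visit at 12 months. Section 8.2 recommends a sample at early withdrawal.

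After the last visit, the one planned contact is a Follow-up Call at least 28 (+10) days later (Sections 7.2.2, 7.3 and 8.2). Its stated purpose is "in order to collect information on the occurrence of adverse events and concomitant medications".

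**The concern.** The definition looks forward 4 weeks from a positive result, while the dose and infusion record ends on the day the last recommended sample is taken. A dose or frequency change made in response to a positive result necessarily comes after that result. For a final-visit sample, it therefore falls in the half of the window that the diary does not reach.

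The same inhibitor could then be classified differently according to whether it was found at month 6 or at the last visit. The registry is descriptive and has no sample-size target (Section 7.6), so the reported number of clinically significant inhibitors is itself the result, and a few reclassified cases could change it. The omission cannot be repaired at the analysis stage, because an analysis plan cannot recover data that were never collected.

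**Working it through.** The protocol gives no figure to reproduce here. The check compares the confirmation window with the end of each data stream.

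**Inputs**
- Window: 4 weeks before and 4 weeks after a positive result, 28 + 28 = 56 days (Section 1).
- Diary dose, infusion and bleed data: end at the completion or withdrawal visit, taken as day 0 of this count (Sections 1 and 7.4.2).
- Follow-up Call: day 28 to day 38 after that visit, reading the (+10 days) as an allowance (Sections 7.2.2, 7.3 and 8.2).
- Call content: adverse events and concomitant medications.

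**Coverage of the dose and frequency route, counting from the sampling date**

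| Sample taken at | Days before test | Days after test | Total |
|---|---|---|---|
| Month 6, subject completes | 28 of 28 | 28 of 28 | 56 of 56 |
| Final or withdrawal visit | 28 of 28 | 0 of 28 | 28 of 56 |

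**Coverage of the other routes after a final-visit sample.** Because the call comes no earlier than day 28, decreased-efficacy adverse events and alternate hemostatic products recorded as concomitant medication can be picked up for 28 of the 28 post-test days. Only the dose and frequency part of criterion 2 lacks a named data source.

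**Tests affected.** On the recommended minimum schedule a completer has post-baseline tests at months 6 and 12, so 1 of 2 is at the final visit. A subject who withdraws before month 6, and whose only post-baseline test is at withdrawal, has 1 of 1. These are counts of tests, not of inhibitors.

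**If the window runs from the date the result is issued.** The definition refers to the result, and the protocol gives no laboratory turnaround. With an assumed turnaround of t days, the diary covers 28 − t of the 56 days:
- t = 0: 28
- t = 7: 28 − 7 = 21
- t = 14: 28 − 14 = 14

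**Coverage if the call also recorded dose and frequency.** Counting from sampling, the post-test part rises from 0 to 28 of 28 days and the whole window from 28 to 56 of 56. Counting from the result, a call on day 28 covers 28 − t of the 28 post-result days. A call on day 38 covers all 28 when t is at most 10, since 10 + 28 = 38.

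**The case against.** The strongest reply is that a positive inhibitor has its own follow-up, which does not stop at the last visit. Section 9.2 gives inhibitor development and lack of effect the same reporting requirements as SAEs. Section 9.3.1 obliges the investigator to pursue enough detail for a full medical assessment. Section 9.1.1 requires follow-up of events related to BeneFIX until they resolve or stabilize. Section 9.1.5 makes a test result that changes dosing reportable as an adverse event. Moreover, criterion 2 asks for a need to increase the dose, a judgement that an investigator can state in a safety report without an infusion diary. An increase needed for efficacy also implies reduced efficacy, which may itself be reported as an adverse event and so meet criterion 1. Finally, Section 7.4.1 mentions factor IX under medication history, so a site might record BeneFIX at the call.

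Most of this stands, and it narrows the point considerably. To be missed, a case must:
- be first positive at the last test;
- have no qualifying sign in the preceding 4 weeks;
- involve no alternate product and no reported decreased-efficacy event;
- have a later dose or frequency increase that appears in neither the call nor the safety report.

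The reply does not close the gap. No section requires dose or frequency to be recorded after the final visit, or says that safety narratives feed the classification. The mention of factor IX in Section 7.4.1 concerns baseline only.

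A reader might go further and infer from the test counts (1 of 2, or 1 of 1) that half or all late inhibitors are misclassified, or that the reported incidence is shown to be biased low. The document supports neither. The counts assume the minimum schedule, whereas visits follow local care. Some confirmation would come from the 4 weeks before the test or from the other routes, and a subject who has stopped BeneFIX has no dose to increase.

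**Conclusion.** The mismatch is real and narrow. For a subject first positive at the completion or withdrawal visit, one of the qualifying routes for a primary safety outcome is not systematically observed in the 28 days after the test. For a month-6 positive in a completer it is observed throughout. The possible error has one direction: an unobserved confirmation can only remove a case from the count.

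How many cases would be lost cannot be computed, since the protocol states no inhibitor rate, number of subjects or laboratory turnaround. The conclusion assumes that the recommended final-visit test is done, that the call is limited to its named content, and that BeneFIX itself is not routinely recorded there as concomitant medication. The change is worth making because it is cheap and has to be made at data collection; the evidence does not show a material bias in the primary result.

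**What to change.** In Sections 7.2.2, 7.3 and 8.2, for subjects with a positive inhibitor result from the Final/Early Termination visit, have the existing Follow-up Call also record BeneFIX dose, frequency and infusions, and bleeds, since that visit. Use these data for the 4-weeks-after part of the definition in Section 1, and state there whether the window runs from the sampling date or the result date. Report any positive whose 4 weeks after the result were not observed as a separate category, not as not clinically significant.

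The cost is protocol wording and a few eCRF fields for what is likely to be a small number of subjects. No visit, test or general diary extension is needed; prolonging the diary for everyone tested at the last visit would be broader than the gap. Dose information gathered at the call relies on recall, so it will be less exact than a diary. The change concerns data collection and classification only and leaves treatment decisions untouched.

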2. RESPONSIBLE PARTIES

Principal Investigator(s) of the Protocol

Name, degree(s)	Title	Affiliation	Address
[name]	Senior Medical Advisor	Medical Affairs, China	[name]
[name]	Senior Director	Clinical Affairs	[name]
[name], MD	[name] of Hematology and Hospital of Blood Diseases, Chinese Academy of Medical Sciences	[name]

ABSTRACT

A Post authorization safety surveillance registry with Benefix in hemophilia B patients in usual care settings

Version of Protocol: Version 1.0

Date of Protocol: 9 July 2013

Main Author: [name], Medical Affairs, China

[name], Clinical Affairs

- Rationale and background

Hemophilia B (congenital factor IX deficiency or Christmas disease) is an X-linked disorder caused by a congenital deficiency of coagulation factor IX clotting activity. Patients with hemophilia B are usually treated by replacing the missing or defective factor IX for treatment or prevention of hemorrhage. BeneFIX received the first regulatory approval on 11 February 1997 in the United States. Presently it is approved in 67 countries and marketed in 43 countries. Reformulated nonacog alfa was approved for use in the EU in July 2007 and since January 2011 only the reformulated version of Nonacog - alfa is being distributed worldwide. The registration trial was conducted in 2008 to support licensure in China. 35 patients with hemophilia B received BeneFIX in this study. It demonstrated that BeneFIX is an efficacious and safe treatment for adult and pediatrics Chinese PTPs and MTPs with hemophilia B. BeneFIX received regulatory approval on 10 July 2012 in China. It's indicated for Control and prophylaxis of bleeding episodes in adult and pediatric patients with hemophilia B;Surgical prophylaxis in adult and pediatric patients with hemophilia B.

A prospective Registry of hemophilia B patients will be conducted to evaluate the safety and efficacy of BeneFIX in the usual treatment of hemophilia B in China.

- Research question and objectives

The registry is to evaluate the safety and efficacy of BeneFIX in hemophilia B patients in the Chinese population.

Primary study objective is to evaluate the product medically important events (FIX inhibitor development, FIX hypersensitivity allergic reaction, thrombogenicity, lack of effect and red blood cell (RBC) agglutination) in Chinese hemophilia B patients during treatment with BeneFIX.

Secondary study objective is to evaluate the overall safety of BeneFIX, including the occurrence of serious adverse events (SAEs), and efficacy.

- Study design

This is a non-interventional, voluntary prospective registry study conducted in major hemophilia treatment centers in China. The registry will enroll Chinese patients of all severities with Hemophilia B. Patients will undergo a screening review prior to enrollment. Enrolled subjects will be treated with intravenous infusions of BeneFIX at a dose and frequency prescribed by the subject's treating physician in accordance with the BeneFIX label and will be adjusted solely according to medical and therapeutic necessity. The registry study will capture observations that will be used for evaluating recombinant FIX replacement product safety, including: subject demographics, medical history, hemophilia history and medications. Safety assessments, treatment data and any laboratory-based FIX inhibitor determinations will be collected at all visits. It is recommended that all subjects in this registry study will be followed for a minimum of 6 months and participation in this registry study will conclude after 12 months.

- Population - "Population" includes the setting and study population

This registry plans to enroll any patient with Hemophilia B in China who is eligible and willing to participate in the registry.

Principle inclusion criteria

Patients must meet all of the following inclusion criteria to be eligible for inclusion in the study:

- 1) Male subjects of all ages and severity with Hemophilia B.
- 2) Subjects using or intending to use BeneFIX for Factor IX replacement therapy.
- 3) Subjects/parents/legal representatives must be able to comply with registry procedures (informed consent/assent process, clinical visits, reporting of infusion and bleed data, reporting of adverse events, etc).
- 4) Evidence of a personally signed and dated informed consent document indicating that the patient (or a legally acceptable representative) has been informed of all pertinent aspects of the study.

Principle exclusion criteria:

Patients meeting any of the following criteria will not be included in the registry study:

- 1) Presence of any bleeding disorder in addition to hemophilia B.
- 2) Treatment with immunomodulatory therapy (e.g., intravenous immunoglobulin [IVIg], routine systemic corticosteroids, cyclosporins, anti-TNF agents).
- 3) Treatment with any investigational agent or device within 30 days prior to the Enrollment Visit.
- 4) Subjects with a past history of, or current factor IX inhibitor. For laboratory-based assessments, any Bethesda inhibitor titer greater than the laboratory's normal range or ≥ 0.6 BU/mL.
- 5) Known hypersensitivity to hamster protein.
- 6) Any condition(s) that compromises ability to collect registry-related observations or that poses a contraindication to registry participation (these conditions include, but are not limited to, inadequate medical history to assure registry eligibility; expectation of poor compliance in provision of observations for registry-related documentation).
- 7) Unwilling or unable to follow the terms of the registry study.

- Variables

Baseline data is including Demographic data , Medical history, Medication history and Hemophilia History.

Treatment Data Collection (Day 0 to 12 months/Early Withdrawal) is including Exposure days, bleed, infusion and response data will be collected throughout the treatment period on the subject diaries. The efficacy outcomes data will be:

- Annualized bleeding rates (ABR) in subjects receiving treatment with BeneFIX,
- The responses to all on-demand treatment with BeneFIX for all bleeds (4 point scale of assessment),
- Number of BeneFIX infusions to treat each new bleed
- Number of spontaneous/non traumatic breakthrough bleeds within 48 hours of a prophylaxis dose of BeneFIX

Safety data collected throughout the treatment period will consist of all AE and SAE data, including product-related medically important adverse events (inhibitor development, FIX hypersensitivity allergic reactions, thrombogenicity, lack of effect and red cell agglutination)

- Data sources

Registry study data will be recorded by a physician/nurse in the medical records, through subject interview and subject diaries, and in the Case Report Forms (CRF).

- Study size

The registry study will be conducted in hospitals and clinics in China. Since the number of potential subjects is unknown, the study is not designed based on sample size considerations

- Data analysis

The results of this study will be presented using descriptive statistics. The primary analysis will be performed on all subjects who receive at least one dose of BeneFIX. The reasons for discontinuation of BeneFIX therapy will be described. Subgroup analysis will be done by several sub-populations, and the details will be in the SAP.

- *Milestones*

Milestone	Planned date
Completion of feasibility assessment.	23 Sep 13
Start of data collection	22 Feb 2014

End of data collection	14 Jul 2016
Study progress report 1	11 Mar 2014, 11 Mar 2015, 11 Mar 2016
Interim report 1	11 Mar 2015, 11 Mar 2016
Registration in the EU PAS register	17 Dec 2013
Final study report	12 Dec 2016

